7.1 Enrollment

Subjects meeting eligibility criteria will be screened by the primary investigator and treating oncologist. Subjects will be introduced to the study during their scheduled oncology and or palliative care visit. Study information will be made available to the subjects. Those interested in the study will be provided with the informed consent, enrolled in the study and provided with the materials necessary for participation in the study.

7.2 Measures of Adherence and Treatment

By using the mobile application, subjects will automatically be keeping a diary that time stamps each entry of pain intensity. Further, the mobile application communicates with Quell and the sham device via Bluetooth and thus also monitors the usage of the device. The questionnaires as stated above will be completed either at the clinic visits as detailed below, or if the subject cannot make it to the clinic visit, the questionnaire will be completed over the phone by the study investigators. The results of these questionnaires will be stored in a HIPAA compliant central data hub.

7.3 Data collection

After informed consent has occurred, all subjects will be asked questions regarding sociodemographics, age, ethnic background, gender, height, weight, medical and related family history (ie. cancer, psychiatric diseases, substance misuse and abuse). Additionally, they will be educated on how to input their pain intensity into the mobile application; and separately how to record their pain medication use using a paper analgesic dairy.

Quality of life assessment will be conducted in person at the enrollment visit (week zero), and again at weeks 6 and 10.

Assessments entered into the mobile application including, pain assessments and sleep monitoring will sync wirelessly through cloud data base and will only be accessed by approved personal directly involved in the study. Anonymized data will be stored in a HIPAA compliant central data hub.

7.3.1 Concomitant Medications

All concomitant medications and concurrent therapies will be documented at screening and each scheduled clinic visit. A CURES report will be retrospectively generated for one month at time of enrollment, then every four weeks for the duration of the study.

7.3.2 Socio-Demographics

Demographic information (date of birth, gender, ethnicity, race) will be recorded at screening

7.3.3 Medical History

Relevant medical history, including history of current disease, pertinent family history, and information regarding underlying diseases will be recorded at Screening.

7.3.4 Vital Signs

Body temperature, blood pressure, pulse and respirations will be performed during their regular scheduled visits and recorded as part of this study. If study visits occur outside of scheduled clinic visits, vital signs will not be performed or recorded.

7.3.5 Adverse events

Information regarding occurrence of adverse events will be captured throughout the study. Duration (start and stop dates and times), severity/grade, outcome, treatment and relation to study drug will be recorded on the case report form (CRF).

7.3.6 Study Visits

Investigators will attempt to schedule study visits so that they coincide with subject's oncology visits in order to not add any additional burden. If these dual visits cannot be scheduled and study visit needs to occur in person, subject will receive compensation for time and travel.

8. Evaluations by Visit

8.1 Visit 1 (Week 0)

- 1. Review the study with the subject and obtain written informed consent and HIPAA authorization.
- 2. Assign the subject a unique screening number.
- 3. Record demographics data.
- 4. Record medical history, including a history of diagnosis date, and prior treatments.

- 5. Record concomitant medications.
- 6. Perform and record vital signs.
- 7. Download and set up mobile application on subject's phone.
- 8. Educate subject on how to use mobile application.
- 9. Have subject demonstrate knowledge of how to use application.
- 10. Perform and record the SF-MPQ-2, opioid assessment and Quality of life Assessment.
- 11. Provide them with their analgesic diary and educate them on how to use it
- 12. Schedule subject for visit 2 weeks.

8.2 Visit 2 (Week 2)

- 1. Record any Adverse Experiences as needed.
- 2. Review Mobile Application Pain assessment.
- 3. Review documentation of analgesic use.
- 4. Perform and record vital signs.
- 5. Give subject Quell/Sham device, make sure subject properly calibrates.
- 6. Educate subject on how to use the device and to adjust intensity if needed and communicate that stimulation should feel "strong but comfortable".
- 7. Schedule follow up phone calls for subject to help trouble shoot and field questions on the device.
- 8. Perform and record the SF-MPQ-2.
- 9. Perform and record the results of the MOS Sleep Scale.
- 10. Schedule follow up visit for 2 weeks.

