Quell is a wearable, automated electrical nerve stimulator designed for people with pain, that includes technology to provide convenience while optimizing pain relief. It consists of four components: a therapy pod, an electrode array, a band, and a mobile app. The therapy

pod, which contains the electronics, is placed in the band and then an electrode array is attached by snapping it to the therapy pod. The electrode array consists of 4 hydrogel pads that provide a large (60 cm2) interface between the stimulator and the patient's sensory nerves. The hydrogel typically lasts 2 weeks or 100 hours of use, and is formulated to reduce skin irritation. The band is placed on the upper calf where therapy is initiated by pressing the button. The reason for placement on the upper calf is that this area has a high density of cutaneous sensory innervation that enables robust stimulation of A β fibers. When placed on the upper calf, the electrode array is circumferential and will stimulate sensory dermatomes S2- L4 providing a broad neural input to trigger analgesia through the descending pain inhibition system.

A calibration procedure is used to estimate the optimal therapeutic stimulation intensity (within the recommended range) for each patient. This is accomplished by an algorithm that automatically determines an intensity within the recommended therapeutic range that is appropriate for the patient. Once calibrated, all subsequent therapy is automatically delivered at the required intensity. The patient has the option of manually adjusting intensity at any time and the device incorporates these changes in subsequent therapy sessions. Quell automatically compensates for nerve desensitization by adaptively increasing the intensity over the course of the one-hour therapy session. The device enables long- term unattended therapy, such as overnight, by automatically restarting hour-long therapy sessions every other hour as long as the device remains on the leg. It also monitors the amount of time it is on the same region of skin and alerts the patient to ventilate the area to reduce the risk of irritation. Finally, Quell has embedded intelligence to determine if the patient is sleeping and automatically reduces the intensity to provide overnight pain relief without disturbing sleep.

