The therapy pod is powered by a Lithium-Ion battery that provides 30-40 hours of therapy (4-7 days of typical use) if fully charged. The battery can be recharged in 2-3 hours by plugging the device into an AC adapter.

3. Study Design

The study is a single site, double blinded, placebo controlled randomized clinical trial. 40 subjects will be selected based on the inclusion criteria stated below and then randomized to either the intervention group or the placebo control group. Prior to the start of this study, a Controlled Substance Utilization Review and Evaluation (CURES) reports will be acquired to establish baseline number of opioid prescriptions for each subject. Subjects will track how consistently they are using pain medications, both opioids and non-opioids, during the two weeks prior to the start of the study. They will also provide twice daily recordings of their pain intensity via a mobile application. At the end of this two-week period, each subject will be fitted with a Quell or a sham device, including initial calibration to the subject's comfort level as described in the background section.

The sham device is identical to Quell in all aspects with one exception. While Quell delivers 1 hour of continuous stimulation during a therapy session, the sham device delivers three 2-minute periods of stimulation at 0, 28 and 58 minutes within the therapeutic session. This limited stimulation should have little to no analgesic effect but should suggest to the subject that they are receiving therapy.

Neither the principal investigator, nor the co-investigator or the subject will know if they are given a sham device or the actual Quell device. The study coordinators will be the only ones who will be aware of which intervention subjects receive. At the end of the study, subjects will be asked if they thought they had the sham or actual device. Both the principal and the co-investigator will be asked to identify which subjects they thought had Quell vs the sham device, prior to analysis of the data.

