11.3 Protocol Violations

A protocol violation occurs when the subject, investigator, or Sponsor fails to adhere to significant protocol requirements affecting the inclusion, exclusion, subject safety and primary endpoint criteria. Protocol violations for this study include, but are not limited to, the following:

- Failure to meet inclusion/exclusion criteria
- Use of a prohibited concomitant medication

• Include other specific examples as appropriate for the study (non-adherence with study drug regimen, etc.)

Failure to comply with Good Clinical Practice (GCP) guidelines will also result in a protocol violation. The Sponsor will determine if a protocol violation will result in withdrawal of a subject.

When a protocol violation occurs, it will be discussed with the investigator and a Protocol Violation Form detailing the violation will be generated. This form will be signed by a Sponsor representative and the Investigator. A copy of the form will be filed in the site's regulatory binder and in the Sponsor's files.

12. Potential Risks

Risk from the device:

Transcutaneous electrical nerve stimulation therapy is considered mostly safe. On rare occasions, an electrical current will be too intense for a subject, causing irritation on the skin. On very rare cases, some subjects have reported some calf muscle cramping with prolonged use.

Some subjects with skin allergies may react to the electrode pads used with the units. People with pacemakers, infusion pumps, defibrillators, and similar devices should not be exposed to the electrical currents produced by transcutaneous electrical nerve stimulation.

Psychological or Social Risks Associated with Loss of Privacy:

In spite of all the safety measures that we will use, we cannot guarantee that the subject's identity will never become known. Every effort will be made to secure the information stored on the mobile application and the information uploaded into the cloud database. In order to maintain subject confidentiality, only a site number, subject number and subject initials will identify all study subjects on any documentation submitted to the Sponsor.

13. Potential Benefits

Subjects enrolled in this study have the potential to have their pain adequately managed while down titrating their overall opioid use. There may be no direct benefit to the subject

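### Both arms are told how stimulation should feel and to adjust it if needed, but the sham is silent for 54 of 60 session minutes, so adjusting in a gap can cue the arm

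*Protocol*

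**What the plan says.** Protocol section 8.2 has a single list of Visit 2 steps for both devices. Item 5 is "Give subject Quell/Sham device, make sure subject properly calibrates". Item 6 is "Educate subject on how to use the device and to adjust intensity if needed and communicate that stimulation should feel" strong, with the qualifier that it stay comfortable. Neither item has arm-specific wording.

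Section 3 describes the sham: "The sham device is identical to Quell in all aspects with one exception". The exception is the delivery pattern. "Quell delivers 1 hour of continuous stimulation during a therapy session", whereas "the sham device delivers three 2-minute periods of stimulation at 0, 28 and 58 minutes within the therapeutic session". The stated purpose of the short bursts is to let the subject believe that treatment is being given, with little or no analgesia.

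Section 2 adds two features of the device. Hour-long sessions restart every other hour while it is worn. Also, "The patient has the option of manually adjusting intensity at any time and the device incorporates these changes in subsequent therapy sessions".

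Section 3 provides weekly check-ins to troubleshoot the device over 8 weeks of use, and asks each subject once, at study end, which device they think they had. Section 4 takes the primary endpoint from a paper diary that the subject fills in.

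**The concern.** A subject who has never worn the device has nothing to compare it with. Item 6 supplies the comparison: it says what treatment should feel like and invites action when it does not feel that way. For a sham subject in a silent gap, that action produces nothing. A control that does not respond is a hint about the arm, and here the protocol's own instruction can prompt it. This works against the purpose that section 3 gives for the bursts.

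The documents show no scripted reply for a subject who says at a weekly check-in that nothing is felt, and no provision for intensity changes made during a gap.

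The outcomes are exposed to this. The subject records the opioid diary, and the pain scores, the SF-MPQ-2, the PGIC and the quality-of-life scale are self-ratings. With about 20 subjects per arm, a few who work out their allocation could matter.

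**Working it through.** The plan states no total on-time or off-time, so the check starts from its schedule.

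**Inputs**
- Sham bursts of 2 minutes starting at minutes 0, 28 and 58 of a 60-minute session (Protocol section 3).
- Active stimulation for the whole 60 minutes (section 3).
- One session every other hour, read as a 120-minute cycle of one hour on and one hour off (section 2).

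**Within a session**
- Sham on: 3 × 2 = 6 minutes. Sham off: 60 − 6 = 54 minutes, and 54/60 = 90%.
- First gap: minutes 2 to 28, so 28 − 2 = 26 minutes.
- Second gap: minutes 30 to 58, so 58 − 30 = 28 minutes. Check: 26 + 28 = 54.
- Active off: 0 of 60 minutes.

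**Over the two-hour cycle**
- Sham off: 120 − 6 = 114 minutes, or 95%.
- Active off: 60 of 120 minutes, or 50%.
- Silence found only in the sham: 114 − 60 = 54 minutes, or 45% of the cycle.

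**What follows from setting the sections side by side**
1. The instruction reaches both arms, because section 8.2 has one list.
2. Manual adjustment exists on the sham, because section 3 makes it identical apart from the burst pattern.
3. A change attempted in a gap produces no sensation at the time, because no current flows.
4. Section 2 says that manual changes are used in later sessions, so a setting raised in a gap may be felt at later bursts. The documents do not say how the sham handles a change made while it is silent, so this step is possible but not established.

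**Direction of bias**
- If sham subjects work out their arm, self-reported outcomes could shift in favour of the device.
- Section 2 also says that analgesia rises with intensity. Stronger sham bursts could therefore give the control some effect and shrink the difference.
- The documents give no rate of adjustment, rate of correct guessing or effect of burst intensity, so neither bias can be sized. The percentages above describe exposure to silence, not bias.

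**The case against.** The strongest reply is that every step is conditional. The subject must be attending during a gap, decide that adjustment is needed, turn the intensity up, and read the lack of response as a sign of sham. Item 5 calibrates the device first, and section 2 says that later therapy then runs automatically at the required intensity. A subject content with the bursts may never touch the control. The comfort qualifier limits upward changes and permits turning down. Item 6 does not say that sensation is continuous, so it can be read as describing stimulation only while it is delivered. Silence is not peculiar to the sham either, since the active device is off for half of each cycle. The gaps come from the sham pattern and would exist without item 6, and the end-of-study guess offers some detection. Consent pages are not in the reviewed text, so what subjects are told elsewhere about sensation is unknown.

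Most of this stands, and it limits the point to a possibility. It does not remove it. Silence within a session occurs only on the sham, the instruction invites the test that can expose it, and the reviewed text has no safeguard. A guess at the end neither prevents unblinding nor shows when it began.

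A reader might also infer harm, because section 12 warns that occasionally "an electrical current will be too intense for a subject, causing irritation on the skin". The documents do not support that step. They call such events rare, do not link them to 2-minute bursts that the subject can turn down, and do not say that a change made in a gap takes effect.

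**Conclusion.** The point holds as a modest weakness in blinding. A common instruction sits badly with a sham that is silent for 54 of every 60 session minutes (90%), and following it in a gap can cue the arm and may alter later bursts.

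Two stronger readings are tempting and go too far:
- **That following the instruction reveals the arm.** The chain is conditional, and the active device also has silent hours.
- **That the result can only be an inflated device effect.** Unblinding and stronger sham bursts push in opposite directions, and neither can be sized. Opposite directions do not make the problem harmless, because nothing ensures that they cancel.

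The conclusion assumes that the sham keeps the manual control, as section 3 implies, that the every-other-hour restart means a 120-minute cycle, and that no arm-neutral explanation is given in the removed consent pages or in a call script outside the documents.

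**What to change.** Add one fixed statement to item 6 of section 8.2, and use the same words in the weekly troubleshooting contacts of section 3: there will be periods while wearing the device when no stimulation is felt. It should be identical in both arms. It is true of both, because the active device is also off every other hour. It should refer to wearing time and not to part of a session, since active stimulation is continuous through the hour.

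Separately, the instruction to "adjust intensity if needed and communicate that stimulation should feel" strong but comfortable must be reconciled with the manual-adjustment text in section 2 and the sham pattern in section 3. The protocol should state how the sham treats a change made while it is silent. The sponsor decides how the adjustment wording reads.

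The cost is one added sentence and a short call script. The downside is small: active subjects may be slightly slower to report a device that has stopped. The app's usage monitoring and the automated alerts in section 3 partly cover this.

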8.3 Visit 3 (Week 4)

- 1. Record any Adverse Experiences/troubleshoot any questions or concerns.
- 2. Review mobile application for adherence use.
- 3. Record changes to concomitant medications.
- 4. Perform and record vital signs.
- 5. Review Mobile Application Pain and Sleep assessment.
- 6. Review documentation of analgesic medication use.
- 7. Perform and record the SF-MPQ-2.
- 8. Schedule follow up visit for 2 weeks.

8.4 Visit 4 (Week 6)

- 1. Record any Adverse Experiences/troubleshoot any questions or concerns.
- 2. Record changes to concomitant medications.
- 3. Review mobile application for adherence use.
- 4. Perform and record vital signs.
- 5. Review Mobile Application Pain and Sleep assessment.
- 6. Review documentation of analgesic medication use.
- 7. Perform and record Quality of life Assessment and SF-MPQ-2.
- 8. Perform and record the results of the MOS Sleep Scale.
- 9. Schedule check in phone calls as needed.
- 10. Schedule follow up appointment in 4 weeks.

8.5 Visit 5 (Week 8)

1. Over the phone unless otherwise scheduled to come into clinic.

- 2. If over the phone only; Review documentation of analgesic use.
- 3. If scheduled to come in; visit 5 will mirror Visit 3 (Week 4).

8.6 Visit 6 (Week 10)

- 1. Record any Adverse Experiences/troubleshoot any questions or concerns.
- 2. Record changes to concomitant medications.
- 3. Review mobile application for adherence of use.
- 4. Perform and record vital signs.
- 5. Review Mobile Application Pain and Sleep assessment.
- 6. Review documentation of analgesic medication use.
- 7. Perform and record SF-MPQ-2 and Quality of life Assessment.
- 8. Collect Quell/Sham device and delete mobile application from subject's phone.
- 9. Administer the PGIC, the MOS Sleep Scale survey and record the results.
- 10. Provide subject with results of any preliminary data analysis pertinent to their involvement in the study.
- 11. Address any remaining question or concerns regarding subject's participation in the study.

8.7 Early Withdrawal Visit

- 1. Record any Adverse Experiences/troubleshoot any questions or concerns
- 2. Record changes to concomitant medications.
- 3. Review mobile application for adherence of use.
- 4. Perform and record vital signs.
- 5. Review Mobile Application Pain and Sleep assessment.
- 6. Review documentation of analgesic medication use.
- 7. Perform and record SF-MPQ-2 and Quality of life survey
- 8. Collect Quell/Sham device and delete mobile application from subject's phone
- 9. Administer the PGIC.
- 10. Provide subject with results of any preliminary data analysis pertinent to their involvement in the study.
- 11. Address any remaining question or concerns regarding subject's participation in the study.

9. Data Storage

All data will be transmitted and stored to HIPAA compliant encrypted standards.

Future research:

Subject information will be kept for at least 2 years after completion of this study and up to 20 years for future research that has not yet been planned. Future research using the data will first be approved by Scripps IRB. After 2031, the code that links the sample to the subject's traditionally-identifying information will be destroyed. Related de-identified health information will be kept indefinitely for future research studies at Scripps in secure databases.

10. Statistical Analysis

A biostatistician will perform all data analysis. The sample size (20 participants per group) achieves 80% power to find a 20% (absolute) difference in mean percent change in opioid consumption between the two groups with an estimated standard deviation of mean percent change of 22% and 90% power with an estimated standard deviation of 19% in both groups using a two-sided two-sample t-test with a significance level (alpha) of 0.05.

Descriptive statistics will be calculated for baseline characteristics of both study groups and to assess the effectiveness of the randomization. Repeated measures analysis will be used to assess changes in opioid medication use, pain assessments, and quality of life mesaures over time in the intervention group compared to the control group. Mid study analysis will be conducted with all data amassed around week 6 of all subjects enrolled.

11. Discontinuation and Replacement of Study Participants

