Change in pain intensity via the mobile app and as described by the subject using the Shortform McGill Pain Questionnaire-2 SF-MPQ-2 and the Patient Global Impression of Change (PGIC). The pain intensity scores will be measured twice daily using the mobile application and the SF-MPQ-2 will be completed during weeks 0,2,4,6 and 10 of the study. The PGIC will come completed at week 10.

These tools were chosen because a treatment should demonstrate a statistically and a clinically significant effect. Well-researched cutoff method suggests, that a 30% reduction of pain can be considered clinically significant (29). This level corresponds with a 2 points on a 0 to 10 pain intensity numerical rating scale (30). The Short-form McGill Pain Questionnaire (SF-MPQ-2) assesses the major symptoms of both neuropathic and nociceptive pain and can be used in studies of epidemiology, natural history, pathophysiologic mechanisms, and treatment response. Numerous studies have demonstrated its reliability, validity, and responsiveness in diverse samples of subjects with acute and chronic pain. Subjects rate their pain in sensory and affective terms and use a visual analog scale. The self-report measure Patient Global Impression of Change reflects a subject's belief about the efficacy of treatment. It is well studied and widely used in chronic pain clinical trials. PGIC is a 7-point scale depicting a subject's rating of overall improvement of a treatment intervention. Subjects rate their change as "very much improved," "much improved," "minimally improved," "no change," "minimally worse," "much worse," or "very much worse."

Changes in quality of life as measured by the Functional Assessment of Cancer The EORTC Quality of Life C-15- PAL measurement scale assessed at time of enrollment (week 0) week 6 and week 10 of the study. This is a validated questionnaire developed to assess the quality of life of palliative care cancer subjects.

Additional analysis includes changes in objective sleep measures using the mobile application and also The Sleep Scale developed for the Medical Outcomes Study. We will also look at the other characteristics of the pain that are automatically monitored with Quell/Sham device and its mobile application such as activity level.

5. Subject Selection

Study Population

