11.1 Early Discontinuation of Quell/Sham Device

A subject may be discontinued from study treatment at any time if the subject, the investigator, or the Sponsor feels that it is not in the subject's best interest to continue. The following is a list of possible reasons for study treatment discontinuation:

- Subject withdrawal of consent (or assent)
- Subject is not compliant with study procedures
- Adverse event that in the opinion of the investigator would be in the best interest of the subject to discontinue study treatment
- Protocol violation requiring discontinuation of study treatment
- Lost to follow-up
- Sponsor request for early termination of study

If a subject is withdrawn from treatment due to an adverse event, the subject will be followed and treated by the Investigator until the abnormal parameter or symptom has resolved or stabilized.

All subjects who discontinue study treatment should come in for an early discontinuation visit as soon as possible and then should be encouraged to complete all remaining scheduled visits and procedures.

All subjects are free to withdraw from participation at any time, for any reason, specified or unspecified, and without prejudice. Reasonable attempts will be made by the investigator to provide a reason for subject withdrawals. The reason for the subject's withdrawal from the study will be specified in the subject's source documents.

Reasonable attempts will be made by the investigator to provide a reason for subject withdrawals. The reason for the subject's withdrawal from the study will be specified in the subject's source documents. As noted above, subjects who discontinue study treatment early (i.e., they withdraw prior to Visit 6) should have an early discontinuation visit. Refer to Section 8 for early termination visit. Subjects who withdraw after Visit 4 but prior to Visit 6 should be encouraged to come in for a final visit (and the procedures to be followed would include those for their next scheduled visit).

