11.2 Replacement of Subjects

Subjects who withdraw from the study treatment will not be replaced, as long some data has been collected from the device. This withdraw will be accounted for in our data analysis. Should subjects withdraw from the study without ever using the device, their device will be collected and they will be replaced with a new participant.

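### The early-visit checklist removes the pain app even from subjects who stop the device but stay in follow-up under 11.1, which ends their twice-daily pain ratings

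*Protocol*

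**What the plan says.** Protocol 11.1 covers everyone who stops the device before the end of the study. Its rule is that they "should come in for an early discontinuation visit as soon as possible and then should be encouraged to complete all remaining scheduled visits and procedures". It repeats the instruction later in the section: "subjects who discontinue study treatment early (i.e., they withdraw prior to Visit 6) should have an early discontinuation visit". For the content of that visit it refers to Section 8, where 8.7 (Early Withdrawal Visit) is the only candidate.

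Item 8 of 8.7 reads "Collect Quell/Sham device and delete mobile application from" the subject's phone. It carries no condition, and no later step puts the app back. The end-of-study visit (8.6 item 8) has the same instruction.

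Protocol Section 4 lists change in pain intensity as a secondary endpoint: "The pain intensity scores will be measured twice daily using the mobile application". Section 3 has this recording begin in the two weeks before the device is fitted: "They will also provide twice daily recordings of their pain intensity via a mobile application". The procedures still to come for a subject who stays include, at week 6 (8.4) and again at week 10 (8.6), "Review Mobile Application Pain and Sleep assessment".

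**The concern.** 11.1 treats stopping the device and withdrawing as the same event, but it also wants people who stop the device to continue the schedule. One checklist then serves two groups. For a subject who leaves the study, deleting the app costs nothing. For a subject who stays, it removes the instrument for a secondary endpoint that 11.1 wants continued, and the later visits ask staff to review app data that are no longer being entered.

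The missing ratings would come from subjects who stopped the device and agreed to go on. They would be missing because of a checklist step, not because of the subject's choice. The phone fallback in 7.2 covers questionnaires and not the twice-daily scores.

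**Working it through.** The plan gives no figure on this point to reproduce. The check is a reading of the sections against each other, followed by a count.

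**Does 8.7 apply to subjects who stay?** 11.1 sends all treatment discontinuers to the early visit and names no other visit for those who continue. A further sentence, "Subjects who withdraw after Visit 4 but prior to Visit 6 should be encouraged to come in for a final visit", adds the procedures of the next scheduled visit. It does not lift the deletion step, and nothing below rests on it.

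**Who could be affected?** 11.1 lists six reasons for discontinuation. Withdrawal of consent, loss to follow-up and early termination by the sponsor would normally end follow-up as well. Non-compliance with study procedures is a weak example, because app entry is itself a study procedure. Adverse event and protocol violation are the plausible cases.

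**Does app entry need the device?** No. The app is set up at week 0 (8.1 items 7 to 9), and the device is issued at week 2 (8.2 item 5). App sleep data do need the device (Section 3) and would stop anyway.

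**Ratings lost per affected subject.** Inputs: two ratings a day (Section 4), device period of 8 weeks within 10 weeks of participation (Section 3).

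- Planned device-period ratings: 8 × 7 × 2 = 112.
- Lost after an early visit at week w: (10 − w) × 7 × 2.

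The weeks are illustrative, since 11.1 sets no fixed time for the early visit. The counts assume that the subject would have stayed to week 10 with full entry. The documents give no entry rate, so 60% to 100% is shown as an assumed range.

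| Early visit | Lost, full entry | Share of 112 | Lost at 60% entry |
|---|---|---|---|
| Week 4 | 42 × 2 = 84 | 75% | 0.6 × 84 = 50.4 |
| Week 6 | 28 × 2 = 56 | 50% | 0.6 × 56 = 33.6 |
| Week 8 | 14 × 2 = 28 | 25% | 0.6 × 28 = 16.8 |

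At a constant entry rate the shares of what would have been entered stay the same.

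**Pain data still scheduled after the early visit.** Section 4 sets SF-MPQ-2 at weeks 0, 2, 4, 6 and 10. Under 8.5, a week 8 visit held in clinic mirrors Visit 3, which includes SF-MPQ-2 (8.3 item 7). QLQ-C15-PAL, with pain items 5 and 12, is due at weeks 0, 6 and 10.

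| Early visit | SF-MPQ-2 left | QLQ-C15-PAL left |
|---|---|---|
| Week 4 | 2 (3 if week 8 is in clinic) | 2 |
| Week 6 | 1 (2 if week 8 is in clinic) | 1 |
| Week 8 | 1 | 1 |

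The early visit itself also collects SF-MPQ-2, quality of life and PGIC (8.7 items 7 and 9), and PGIC is due again at week 10 (8.6 item 9).

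**The case against.** The strongest reply is that 8.7 is an exit visit. Its title says withdrawal, it copies the closing steps of Visit 6, and 11.1 glosses the group as subjects who withdraw before Visit 6. On that reading deletion is correct. This stands for subjects who leave. It does not remove the conflict for those who stay, because 11.1 sends them to the same visit and gives them no other.

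Four stronger readings are tempting, and the documents do not support them.

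- A reader might infer that these subjects can no longer record pain at all. The phone is their own, eligibility requires that they can download an app, and staff set the app up at week 0, so it could be reinstalled. What can be said is that no step provides for this.
- A reader might infer from 11.2 ("Subjects who withdraw from the study treatment will not be replaced, as long some data has been collected from the device") that the non-replaced subjects are the ones who stay in follow-up. The rule in 11.2 turns on whether the device was used and yielded data. It does not say who continues.
- A reader might infer that the partial series is lost. Entries sync to a cloud database (7.3), and the mixed model in SAP 2.5 can use those made before deletion. SAP 2.5 also compares all participants with those who have complete data. Neither analysis restores later ratings, but incomplete data were considered.
- A reader might infer harm to the primary endpoint. Opioid use is recorded in a paper diary (Section 4), which 8.7 does not stop.

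**Conclusion.** The conflict between 8.7 item 8 and 11.1 is real, and the point is minor. Followed as written, 8.7 ends one secondary endpoint, the twice-daily app pain score, for any subject who stops the device and stays in follow-up. The ceiling per affected subject is 75%, 50% or 25% of the device-period ratings for an early visit at week 4, 6 or 8, provided the subject would have continued to week 10 with full entry.

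The documents give neither a discontinuation rate nor the share of discontinuers who stay. The number affected may therefore be zero, and no loss for the trial as a whole or bias in the treatment comparison can be computed or claimed. The other scheduled pain and quality-of-life assessments continue, though at a few occasions and not twice a day.

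**What to change.** Reconcile 8.7 with 11.1 by making the deletion conditional. The device is collected at the early visit, as 8.7 already says. The app is deleted there only if the subject is leaving the study. For a subject who agrees to further follow-up, app pain entry continues to week 10, the app is deleted at Visit 6, and the scores enter the planned repeated measures analysis of pain. No change to 8.6 or to the primary endpoint is needed.

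The cost is a change of checklist wording, with no new instrument or visit. The downside is the burden of continued twice-daily entry for subjects who agreed to follow-up. SAP 2.5 is written in the past tense. If data collection has already ended, the remaining step is to report how many subjects stayed in follow-up after the app was deleted, and to state that their later app scores are missing because of the procedure.
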